1.6. Changes to Planned Analyses

Since laboratory samples are only collected at screening and pre-dose 2 timepoints, and vital signs are only measured at screening and pre-dose, no summary tables per time point will be created even though the analyses were planned in the protocol.

Since the percentile for length is a less useful clinical parameter for children less than 24 months, the analysis of the percentile for length will not be done.

2. GENERAL ANALYSIS DEFINITIONS

All types of analysis together with the description of rules for handling missing or incomplete data are described later in this document. These analyses will include vaccinated participants with respect to the actual vaccine administered (ie, Ad26.ZEBOV as Dose 1 followed by MVA-BN-Filo as Dose 2 or MenACWY as Dose 1 followed by another MenACWY as Dose 2). Also, participants who receive only the first vaccination (Ad26.ZEBOV or MenACWY) will be included in accordance with the intervention arm with that first vaccination. Otherwise, the participant will be excluded from summary tables and graphs but will be included in listings. For instance, a participant who will receive MVA-BN-Filo as Dose 1 will not be included in summary tables and graphs.

In general, the study data will be analyzed as follows:

- Categorical variables will be summarized with a frequency table presenting counts and percentages.
- Continuous variables will be summarized using the following statistics, as appropriate: number of observations, arithmetic mean, geometric mean, corresponding 95% CI, standard deviation, standard error, median, quartiles (Q1 and Q3), minimum and maximum.

Baseline value will be defined as the value of the last available assessment performed prior to the first vaccination (Dose 1) on Day 1, unless specified otherwise.

For safety assessments, the *baseline value* will be an assessment performed prior or on the date (if only time of assessment is missing) of the first vaccination. The baseline value for immunogenicity assessments will be an assessment performed before or on the date of the first vaccination. In case of multiple values, the value closest to the vaccination will be used as the baseline.

Visit day will be determined relative to the actual day of vaccination (ie, date of Dose 1 or Dose 2).

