11.1. Analysis Sets

Full Analysis Set: The full analysis set will include all randomized participants with at least one study intervention administration documented. Participants will be analyzed according to the intervention they actually received.

Per-protocol Immunogenicity Population: The per-protocol immunogenicity population will include all randomized and vaccinated participants for whom immunogenicity data are available excluding participants with major protocol deviations expecting to impact the immunogenicity outcomes (eg, missed vaccinations, natural infections, etc).

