2.3. Analysis Sets

Vaccination assignment will follow the "as treated" principle. That is, participants will be analyzed according to the actual intervention received.

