2.3.1. Full Analysis Set (FAS)

The full analysis set will include all participants with at least one study intervention administration documented.

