5. SAFETY

Safety analyses will be performed on the full analysis set. Continuous variables will be summarized using the following statistics, as appropriate: number of observations, arithmetic mean (mean), 95% CI for the mean, standard deviation (SD), standard error (SE), median, quartiles (Q1 and Q3), minimum and maximum. Frequencies and percentages (one decimal place) will be generated for categorical variables. No formal comparisons between groups will be provided.

The safety data will be presented by vaccine regimens (ie, intervention arms) as described in the study protocol. The data will be presented by analysis period (post-dose 1 and post-dose 2) as well as over the entire regimen period (ie, combined post-dose 1 and post-dose 2 periods). Denominator for the percentages will be the number of participants in the considered population and period/phase for a certain regimen (eg, incidence per 100 participants/period).

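### SAP section 2 drops mixed-sequence infants from every summary table, so a wrong Dose 2 also removes valid post-dose-1 safety data

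*SAP*

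**What the plan says.** SAP section 2 sets out, for all analyses, which vaccinated infants are tabulated. It keeps three patterns: Ad26.ZEBOV then MVA-BN-Filo; MenACWY then MenACWY; and a single first dose of either Ad26.ZEBOV or MenACWY. On the third it states that "participants who receive only the first vaccination (Ad26.ZEBOV or MenACWY) will be included in accordance with the intervention arm with that first vaccination". For everyone else: "Otherwise, the participant will be excluded from summary tables and graphs but will be included in listings". One example is given: "a participant who will receive MVA-BN-Filo as Dose 1 will not be included in summary tables and graphs".

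Other sections carry no condition on sequence:

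- Protocol 11.1: "The full analysis set will include all randomized participants with at least one study intervention administration documented".
- SAP 2.3.1: "The full analysis set will include all participants with at least one study intervention administration documented".
- SAP 2.3, on assignment: "participants will be analyzed according to the actual intervention received".
- SAP section 5: "Safety analyses will be performed on the full analysis set", and "The data will be presented by analysis period (post-dose 1 and post-dose 2) as well as over the entire regimen period". It takes percentage denominators from the population and period concerned.

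SAP Table 3 closes the post-dose-1 period no later than one minute before the post-dose-2 period opens.

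**The concern.** An infant given Ad26.ZEBOV then MenACWY, or MenACWY then MVA-BN-Filo, received neither full regimen and did not stop after Dose 1. Such an infant therefore falls under the exclusion. No later SAP section returns the infant to the safety tables.

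The result is uneven. Take two infants with the same correct Dose 1, one of whom misses Dose 2 while the other receives the wrong vaccine as Dose 2. Their post-dose-1 data are equally valid, because the period ends before Dose 2 is given. Yet the first infant is tabulated and the second is not.

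Safety is the primary objective, and its main summary is the number and percentage of infants with each event by arm. The sample-size section describes what could be concluded from seeing no events. Leaving out a correctly exposed infant, and possibly the only event of its type, therefore affects the count that matters most here.

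**Working it through.** **1. Which sequences are tabulated under SAP section 2**

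| Dose 1 | Dose 2 | Summary tables |
|---|---|---|
| Ad26.ZEBOV | MVA-BN-Filo | kept |
| MenACWY | MenACWY | kept |
| Ad26.ZEBOV or MenACWY | none | kept, in the Dose 1 arm |
| Ad26.ZEBOV | MenACWY | listings only |
| MenACWY | MVA-BN-Filo | listings only |
| MVA-BN-Filo | any | listings only (the SAP's own example) |

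Rows 4 and 5 are the problem. These infants are in the full analysis set and have a complete, correctly exposed post-dose-1 period, so SAP section 5 would count them in the post-dose-1 table. In the last row no arm column exists for the infant, so the arm-specific safety columns are unaffected.

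**2. The plan's own figures**

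The sentinel cohort of 16 is split 1:1, giving 8 + 8. The remaining 107 − 16 = 91 are split 5:2, giving 65 + 26. The arms are 8 + 65 = 73 and 8 + 26 = 34, as in Protocol Table 2.

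The exact one-sided 95% upper bound with zero events is 1 − 0.05^(1/n):

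- n = 73: 4.02% (Protocol 11.2 states 4.0%)
- n = 34: 8.43% (Protocol 11.2 states 8.4%)

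The one-sided bound is the one the protocol uses; the two-sided form, 1 − 0.025^(1/n), would give 4.9% and 10.3%.

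**3. One excluded infant with no event**

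- Ebola arm, n = 72: 1 − 0.05^(1/72) = 4.08%, up 0.06 points
- Control arm, n = 33: 1 − 0.05^(1/33) = 8.68%, up 0.25 points

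The documents give no expected number of dosing errors. Taking one to five such infants per arm as an assumed range, the bound runs from 4.08% to 4.31% in the Ebola arm (n = 72 to 68) and from 8.68% to 9.81% in the control arm (n = 33 to 29).

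**4. One excluded infant with the arm's only post-dose-1 event of a type**

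With one event, the exact one-sided bound is the p that solves (1 − p)^n + n·p·(1 − p)^(n−1) = 0.05.

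| Arm | Infant counted | Bound | Infant excluded | Bound |
|---|---|---|---|---|
| Ebola | 1/73 = 1.4% | 6.3% | 0/72 | 4.08% |
| Control | 1/34 = 2.9% | 13.2% | 0/33 | 8.68% |

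These counts are for the post-dose-1 table. The whole-regimen table combines both post-dose periods, so it shows the same zero only if no other infant in that arm has the event after Dose 2.

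**The case against.** The best defence is that the rule was written for a wrong Dose 1. That is the SAP's only example, and listing such an infant separately is reasonable. SAP section 5 is the more specific text on safety, so a programmer might follow it and count the infant anyway. The intention may well have been narrower, but the wording does not say so. If it is read narrowly, a mixed sequence has no stated handling at all.

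It is also fair that the effect is contingent and usually negligible. The protocol provides matching kits assigned by the interactive system, a dedicated unblinded preparer and an independent study intervention monitor. No hypothesis is tested, so no decision threshold moves. This stands, and it limits the priority.

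Three stronger readings are tempting, and the documents do not support them:

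- **That the rule contradicts the full analysis set definition.** Both definitions govern membership, and SAP section 2 removes nobody from the set; it limits what is displayed. The conflict is with SAP section 5.
- **That this is an undeclared departure which SAP 1.6 had to list.** Protocol section 11 leaves specific details to the SAP, and Protocol 11.4 does not say how to place a mixed sequence.
- **That the data are lost.** All adverse events appear in listings, and SAP 5.1.2 provides listings or narratives, as appropriate, for deaths, severe or serious events and discontinuations of vaccination due to an event. What they do not supply is the count and percentage by arm.

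**Conclusion.** The point holds as a minor one. As worded, SAP section 2 gives a wrong post-dose-1 safety count whenever an infant receives a correct Dose 1 and a wrong Dose 2, and it disagrees with SAP section 5.

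Without a dosing error there is no effect. With one affected infant and no event, the loss of precision is trivial. The case worth guarding against is a single event of its type that disappears from the post-dose-1 table. It needs a dosing error and a sole event in the same infant, and the documents give no basis for a probability.

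A reader might infer that the whole-regimen table always loses the event too; it does so only under the condition given in the working. All figures assume the planned arm sizes of 73 and 34.

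**What to change.** Amend the paragraph in SAP section 2 as follows:

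1. State that the exclusion does not apply to post-dose-1 safety tables. Every infant given Ad26.ZEBOV or MenACWY as Dose 1 is counted there, in the arm of that Dose 1.
2. Show events after a wrong Dose 2, including serious adverse events, in a separate other-sequence row, column or footnote. Do the same for all data of an infant given MVA-BN-Filo first. Give the number of full-analysis-set infants concerned.
3. For whole-regimen tables, state by footnote how such infants are counted, so that the denominator and the events refer to the same infants.

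It would not be enough to say that these infants are handled exactly like those with a first dose only. SAP 5.1.1 tabulates serious adverse events over the whole study, so a first-dose-only infant's later serious events stay in the Dose 1 arm, whereas those after a wrong Dose 2 need a stated place.

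The cost is one SAP paragraph and, only if such a case occurs, one row, column or footnote. No new data are needed. The wording should be settled before unblinding, so that placement is not chosen with knowledge of the infant's events.

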2.1. Analysis Periods/Phases

Because the analysis of adverse events (AEs) will be presented per period (and not per time point), these will be assigned to the analysis periods based on Table 3 for the main study, and on Table 4 for the extension phase.

For the analysis that will be presented by time point (e.g. immunogenicity data), the electronic case report form (eCRF) visit schedules will be used for the post baseline assessments as follows:

- For the analysis based on the per protocol set, only assessments that fall within the protocol defined visit window will be used.
- For other analyses based on the full analysis set (if applicable), the assessments that fall outside the protocol defined windows will also be included. If only unscheduled visits are present for a time point, then the one closest to the scheduled visit will be used. If distances of multiple assessments to the scheduled visit are equal, the measurement with the latest date will be used.

		Interval			
Phase	Period	From	То		
Screening		Date and time of signing the informed consent form	One minute prior to start of post dose 1 period		
Regimen	Post-dose 1	Date and time of first vaccination	 Minimum of: a) 23:59 on the date of last contact (for early discontinuation) b) 23:59 on the date of database cut-off date in case of interim c) 23:59 of 28 days after the first vaccination (23:59 of day of vaccination + 28 days) d) One minute prior to post-dose 2 period 		
Follow-up 1		One minute after post-dose 1 period ends	 Minimum of: a) 23:59 on the date of last contact (for early discontinuation) b) 23:59 on the date of database cut-off date in case of interim c) One minute prior to post-dose 2 period 		
Regimen	Post-dose 2	Date and time of second vaccination	 Minimum of: a) 23:59 on the date of last contact (for early discontinuation) b) 23:59 on the date of database cut-off in case of interim analysis c) 23:59 of 28 days after the second vaccination (23:59 of day of vaccination + 28 days) 		
Follow-up 2		One minute after post-dose 2 period ends	 Minimum of: a) 23:59 on the date of last contact (for early discontinuation) b) 23:59 on the date of database cut-off in case of interim analysis c) 23:59 on the date of last study visit 		

Table 3: Analysis Period Definitions (Main Study)

		Interval		
Phase	Period	From	То	
eFollow-up 2		One minute after Follow-	One minute prior to signing the informed consent	
		up 2 phase ends	form	
eScreening		Date and time of signing the informed consent form	One minute prior to start of post dose 1 period	
eRegimen	ePost-dose 1	Date and time of first	Minimum of:	
		vaccination	e) 23:59 on the date of last contact (for early discontinuation)	
			f) 23:59 of 28 days after the first vaccination	
			(23:59 of day of vaccination + 28 days)	
			g) One minute prior to ePost-dose 2 period	
eFollow-up 1		One minute after ePost-	Minimum of:	
		dose 1 period ends	d) 23:59 on the date of last contact (for early	
			discontinuation)	
			e) One minute prior to ePost-dose 2 period	
eRegimen	ePost-dose 2	Date and time of second	Minimum of:	
		vaccination	d) 23:59 on the date of last contact (for early	
			discontinuation)	
			e) 23:59 of 28 days after the second	
			vaccination (23:59 of day of vaccination +	
			28 days)	
eFollow-up 2		One minute after ePost-	Minimum of:	
		dose 2 period ends up to 28	d) 23:59 on the date of last contact (for early	
		days after last post-dose.	discontinuation)	
			e) 23:59 on the date of last study visit	

Table 4: Analysis Period Definitions (Extension Phase)

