- h. Prior to study intervention administration and at the end of the observation period.
- i. Diaries will be completed at home by either a project field worker who will visit the participant during daily visits or by the parent(s)/guardian to document symptoms of solicited local and systemic adverse events in the evening after each vaccination and then daily for the next 7 days at approximately the same time each day.
- j. After the first and second vaccination, participants will remain under observation at the study site for at least 30 minutes for presence of any acute reactions, or longer if deemed necessary by the investigator. Solicited local and systemic and unsolicited adverse events emerging during the observation period will be recorded in the CRF.
- k. Solicited adverse events will be documented in the evening after the first and second vaccination and then daily for the next 7 days, during daily home visits by a project field worker.
- 1. Serious adverse events and/or special reporting situations that are related to study procedures or that are related to non-investigational (concomitant) sponsor products will be reported from the time a signed and dated ICF is obtained onwards until the end of the study. All other serious adverse events and/or special reporting situations will be reported from the day of the first vaccination onwards until 28 days post-dose-2. At the screening visit participants will also be asked about serious adverse events that occurred between the D365 follow-up visit of the main phase and the start of the extension phase. These will be recorded on the AE form.
- m. Concomitant therapies must be recorded from screening onwards until 28 days post-dose-1 and from the second vaccination until 28 days post-dose-2. At the other time points, it should only be recorded if given in conjunction with serious adverse events.

CONFIDENTIAL – FOIA Exemptions Apply in U.S.

ABBREVIATIONS

Adxx adenovirus serotype xx (vector)

Ad26.ZEBOV adenovirus serotype 26 expressing the Ebola virus Mayinga glycoprotein

AE adverse event

BN Bavarian Nordic GmbH CI confidence interval

COMAHS College of Medicine and Allied Health Sciences

CRF case report form

DMID Division of Microbiology and Infectious Diseases

EBOV Ebola virus

eDC electronic data capture

EDTA ethylenediaminetetraacetic acid

eDx extension Day x

ELISA enzyme-linked immunosorbent assay EPI Expanded Program on Immunization

EU European Union

EUA Emergency Use Authorization

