1.2.2. Extension Phase

After the last participant has completed the 12 months post-dose-1 visit or left the study (ie, completion of the main study), there will be an interim database lock and unblinding of the study. Subsequently, participants in the control group who have not withdrawn during the main study, will be offered the Ebola vaccine regimen in an optional extension phase of the study. Participants opting to receive the vaccine regimen will be followed-up for safety until 28 days post-dose-2. No immunogenicity assessments will be performed in the extension phase.

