4.2. Disposition Information

For both main study and extension phase, the number and percentage of participants screened, participants in the full analysis set, participants vaccinated but not randomized, participants randomized but not vaccinated, participants who received MenACWY as third vaccination, participants who completed (study completion and vaccination completion) and discontinued participants (study discontinuation and vaccination discontinuation) with the reason of discontinuation will be tabulated per intervention arm and overall. Also, the number of participants and percentage in each analysis period will be tabulated.

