5.1.2. Analysis of Adverse Events

Number and percentage of participants with at least one particular AE (unsolicited/solicited) will be tabulated. Unsolicited AEs will be summarized by System Organ Class and Preferred Term. Solicited AEs will be summarized by class (local, systemic) and preferred term.

The following tables will be generated for solicited AEs: summary, by worst severity grade, at least Grade 3, related (systemic only), time to onset (in days) and duration (in days) for most frequent events and body temperature. Note that duration is defined as number of days from the start of the event until resolution of the event. The time to first onset is defined as (date of first onset – reference date + 1). The reference date is the start date of the vaccination period.

For unsolicited AEs, the following tables will be generated: summary table (including SAE, AE with fatal outcome, AEs leading to study discontinuation, and AEs leading to discontinuation of study vaccination), all events, most frequent, grade 3, permanent stop of vaccination, related and SAE.

Listings and/or participant narratives will be provided as appropriate, for those participants who die, discontinue study vaccinations due to an AE, or experience a severe or serious AE.

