5.1.3. Phase allocation of Adverse Events

Solicited events are always allocated to the respective Post Dose period. Adverse events in the SDTM database are allocated to periods based on their start date/time. If the start date/time of an event falls between (or on) the start and stop date/time of a period, the AE is attributed to that period (treatment-emergent principle). A stepwise approach to allocate adverse events to the analysis periods/phases based on their start date/time is given in Attachment 2.

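### SAP Table 4 gives the name eFollow-up 2 to two separate intervals, one before any Ebola vaccine and one after extension dose 2, so extension outputs made by that label would pool them

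*SAP*

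**What the plan says.** SAP Section 2.1 assigns adverse events to analysis periods by Table 3 in the main study and by Table 4 in the extension. Two rows of Table 4 are called eFollow-up 2:

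- **First row.** It starts one minute after main-study Follow-up 2 ends. Its end is given as "One minute prior to signing the informed consent" form.
- **Last row.** It starts one minute after ePost-dose 2 ends; the entry contains the words "dose 2 period ends up to 28" and goes on to days after the last dose period. It stops at the earlier of last contact and last study visit.

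The extension follows completion and unblinding of the main study (SAP 1.2.2): "Subsequently, participants in the control group who have not withdrawn during the main study, will be offered the Ebola vaccine regimen".

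Several outputs use these periods in both phases. SAP 4.2 says "the number of participants and percentage in each analysis period will be tabulated". SAP 4.5 tabulates concomitant therapies per analysis period. SAP 5 takes percentage denominators from the period or phase.

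On SAEs, the Protocol's extension Time and Events Schedule (SAE footnote) has sites ask at extension screening about "serious adverse events that occurred between the D365 follow-up visit of the main phase and the start of the extension phase", and adds: "These will be recorded on the AE form". SAP 5.1.3 states: "Adverse events in the SDTM database are allocated to periods based on their start date/time". The unsolicited-event tables listed in SAP 5.1.2 are "all events, most frequent, grade 3, permanent stop of vaccination, related and SAE", after a summary table. SAP 5.1.1 exempts SAEs from the 28-day limit, tabulates them across the whole study, and tabulates the two phases separately.

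**The concern.** A period label should identify one stretch of time at one exposure status. Here the same label covers children who have so far had only the control vaccine and children who have completed both extension doses. A table grouped or filtered by that label cannot tell them apart.

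Two kinds of output are exposed. The first is anything made per period in the extension: participant counts, concomitant therapies and period denominators. A child who stops after extension dose 1 would still be counted under eFollow-up 2 because of the first row. The second is the extension SAE table, where an event in a child who had received only MenACWY could be shown in the output describing the Ebola regimen.

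**Working it through.** **Step 1. Do the two rows overlap?** In Table 4 the order is: eFollow-up 2 (first row), eScreening, ePost-dose 1, eFollow-up 1, ePost-dose 2, eFollow-up 2 (last row). Four intervals lie between the rows that share a name, so they are disjoint. The first row is wholly before any Ebola vaccine: it ends before extension consent, and Protocol 4.2.2 excludes children who have had an Ebola vaccine. The start and end entries of the two rows differ, so this is not one row printed twice.

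**Step 2. How much time does the last row hold?** Inputs: ePost-dose 2 ends at 23:59 on the day of dose 2 + 28 (SAP Table 4); the final visit is at eD85 ±7 days, that is dose 2 + 28 ±7 (Protocol, extension Time and Events Schedule); visits after a dose are timed from the actual vaccination day (same schedule, note).

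Days in last row = max(0, last visit day − first day of row + 1), where the first day of the row is dose 2 day + 29.

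| Dose 2 | ePost-dose 2 ends | Last row starts | Earliest, planned and latest visit | Days in last row |
|---|---|---|---|---|
| eD50 | eD78 | eD79 | eD71, eD78, eD85 | 0, 0, 7 |
| eD57 | eD85 | eD86 | eD78, eD85, eD92 | 0, 0, 7 |
| eD64 | eD92 | eD93 | eD85, eD92, eD99 | 0, 0, 7 |

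For eD57 and the latest visit: 92 − 86 + 1 = 7. With in-window visits the row holds 0 to 7 days, and it is empty for any child whose last visit is on or before dose 2 + 28 days. If the 28-day wording in that row is read as a cap counted from dose 2, the row is always empty.

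**Step 3. How much time does the first row hold?** The documents give no length. For an entrant who reached main-study Follow-up 2, it spans the wait for the last participant's 12-month visit, the interim lock and unblinding, and then consent. Wherever this exceeds 7 days, most of the time under the shared label is pre-vaccine; where the last row is empty, all of it is.

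**Step 4. Where does an SAE from the gap go?** It is asked for at extension screening and put on the AE form. Allocation by start date places it in the first row of Table 4. Three SAP statements then bear on tabulation: Table 4 governs the extension, SAEs are tabulated across the whole study, and each phase is tabulated separately. Read together, they put every Table 4 row, including the gap, into the extension SAE table. No sentence says so outright, and none excludes the gap.

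**Step 5. Scale.** There are 34 planned controls (Protocol Table 2, SAP Table 2). One child with a gap SAE adds 1/34 = 0.029, or 2.9 percentage points, if all 34 enter (Clopper-Pearson 95% CI for 1/34: 0.1% to 15.3%). If only 20 enter (an assumption), it adds 1/20 = 5.0 points (0.1% to 24.9%). The documents give neither the gap length nor an SAE rate for it, so the expected number of such events cannot be computed.

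**The case against.** **Follow-up rows may not be analysis periods.** In Table 4, eFollow-up 2 stands in the Phase column with the Period cell blank, and SAP 5 spells out analysis period as post-dose 1 and post-dose 2. On that reading the count in SAP 4.2 leaves out both rows. Usage is not consistent, since SAP Attachment 2 calls Screening a period. This stands as a condition on the pooling of counts.

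**The start of SAE reporting is not absent.** The SAP's extension SAE endpoint gives an end and no start, so a reader might infer that the window has no defined beginning. The documents do not support that. The same protocol footnote starts reporting of all other extension SAEs at the first vaccination, the SAP refers to the protocol for detail, and the main-study SAE endpoint is worded in the same way. However, the footnote governs collection, and it adds the gap SAEs to what is collected.

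**Extension outputs are for children receiving the Ebola regimen.** SAP 5.1.1 says this, and it sits badly with showing gap events there. But it selects children, not time: a child with a gap SAE who is later vaccinated still qualifies.

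**For SAEs there is little to mix.** The last row holds at most 7 days, and SAE collection generally ends 28 days after dose 2. This is correct. The issue for SAEs is therefore less the blending of two intervals than a pre-vaccine interval carrying a post-dose-2 name inside the extension table.

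**Dates separate the cases.** They do, in listings and in the data. The tables still need a rule.

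**Conclusion.** Wrong as written, and minor. The duplicated label is certain from the text. The pooling of per-period outputs follows if analysis periods include the follow-up rows; the pooled label would then be mostly or wholly pre-vaccine time, assuming in-window final visits and a gap longer than 7 days. Placement of gap SAEs in the extension SAE table follows from reading three SAP statements together. The size is 2.9 percentage points for one such child if all 34 planned controls enter, and more if fewer do.

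Three stronger readings are not supported:

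- A reader might infer that the SAP instructs analysts to count gap SAEs as events under the Ebola regimen. It has no such sentence, and two statements point the other way.
- A reader might size the pooled participant count from retention to the final visit. A child who completes on or before dose 2 + 28 days contributes no time to the last row, so retention does not measure it.
- A reader might infer that the safety results are contaminated more widely. The ePost-dose 1, ePost-dose 2 and combined-regimen tables are defined without either row, and no main-study result changes. Extension safety is exploratory and descriptive.

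**What to change.** 1. In SAP Table 4, give the first row its own name, for example Inter-phase, pre-extension, and keep eFollow-up 2 only for time after ePost-dose 2.
2. In SAP 5.1.1, state that SAEs with onset before ePost-dose 1 (gap and eScreening) are shown separately from SAEs with onset after extension vaccination.

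While the table is open, it would help to say what the 28-day wording in the last row is counted from, and whether the counts in SAP 4.2 include follow-up rows.

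The cost is one row name, one sentence and a few lines of period derivation, done before the final database lock. No new data are needed.
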